6.3.3. Non-Responder Imputation

The non-responder imputation (NRI) method will be used to implement the composite strategy [ICH E9(R1)] for handling intercurrent events. This strategy is used to assess the combination of the effect of the study treatment with the occurrence of an intercurrent event. In this strategy patients are defined as responders only if they meet the clinical requirements for response at the predefined time AND they remain on the assigned study treatment. Failing either criteria by definition makes them nonresponders.

Patients will be considered non-responders for the NRI analysis if they do not meet the clinical response criteria or have missing clinical response data at the analysis time point. Enrolled patients without at least 1 observation within Study AMAH will also be defined as nonresponders for the NRI analysis. Analysis of binary categorical efficacy and health outcome variables may be assessed using an NRI method.

6.3.4. Modified Non-responder Imputation

The modified non-responder imputation (mNRI) method will be used to implement the composite strategy [ICH E9(R1)] for handling intercurrent events. This strategy is used to assess the combination of the effect of study treatment with the occurrence of an intercurrent event. For the mNRI method, the patient's response status is defined based on if the patient meets the clinical requirements for response at the predefined time AND the treatment-related contraindication reasons of discontinuation. The outcomes after the discontinuation for treatment-related reasons are considered failure/nonresponse, as in nonresponder imputation (NRI). Discontinuation for reasons that are considered unrelated to study treatment will not be considered a contraindication, thus the resulting outcomes will be imputed by MI. Patients will be considered as non-responders for the mNRI analysis at the analysis time point if they do not meet the clinical response criteria or have missing clinical response data due to discontinuation from study treatment with a reason of adverse event (AE) including death, or lack of efficacy. For patients discontinuing treatment with any other reason, the MI method (Section 6.3.2) will be used. The mNRI method will be the primary analysis method for categorical efficacy and health outcome variables.

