7.4. Dosage Modification

After Study AMAH dosing is no longer blinded, patients who in the opinion of the investigator have experienced significant clinically meaningful loss of efficacy during study participation may be increased from 125 mg mirikizumab Q8W to 250 mg mirikizumab Q8W if it is determined by the patient and the investigator that the patient might benefit from additional study drug in order to maintain satisfactory disease control. All patients who increase dosing to 250 mg mirikizumab Q8W will remain on this dose until completion of the study or early discontinuation. No other dose adjustments are permitted in Study AMAH.

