 - The patient develops a malignancy (note: patients may be allowed to continue if they develop no more than 2 non-melanoma skin cancers during a 12-month period).
 - Any patient who has a change in disease phenotype at any time (for example, a change to pustular psoriasis).
 - It is recommended that the patient be assessed by an appropriately trained professional to assist in deciding whether the patient is to be discontinued from study treatment if:
 1. The patient, at any time during the study, scores a 3 for Item 12 (Thoughts of Death or Suicide) on the 16-item Quick Inventory of Depressive Symptomatology (QIDS-SR16);OR
 2. The patient develops active suicidal ideation with some intent to act with or without a specific plan (“yes” to Question 4 or 5 on the “Suicidal Ideation” portion of the Columbia-Suicide Severity Rating Scale [C-SSRS])OR

3. The patient develops suicide-related behaviors as recorded on the C-SSRS.
 - The patient develops active TB or HIV/AIDS during the study.
 - The patient becomes HBV DNA positive or hepatitis C virus (HCV) ribonucleic acid (RNA) positive. The patient should be referred to a specialist physician (see Sections 8.1.2 and 9.4.5.3 for HBV, and Section 9.4.5.4 for HCV).
- Patients will also be permanently discontinued from study drug, complete the Post-Treatment Follow-up, and then permanently discontinue from the study in the following circumstances:
 - Enrollment in any other clinical study involving an investigational product or enrollment in any other type of medical research judged not to be scientifically or medically compatible with this study
 - Participation in the study needs to be stopped for medical, safety, regulatory, or other reasons consistent with applicable laws, regulations, and Good Clinical Practice (GCP)
 - Investigator decision
 - The investigator decides that the patient should be discontinued from the study
 - If the patient, for any reason, requires treatment with another therapeutic agent that has been demonstrated to be effective for treatment of the study indication, discontinuation from the study occurs prior to introduction of the new agent

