9.2. Adverse Events

Investigators are responsible for monitoring the safety of patients who have entered this study and for alerting Lilly or its designee of any event that seems unusual, even if this event may be considered an unanticipated benefit to the patient.

The investigator is responsible for the appropriate medical care of patients during the study.

Investigators must document their review of each laboratory safety report.

The investigator remains responsible for following, through an appropriate health care option, AEs that are serious or otherwise medically important, considered related to the investigational product or the study, or that caused them to discontinue the investigational product before completing the study. The patient should be followed until the event resolves, stabilizes with appropriate diagnostic evaluation, or is reasonably explained. The frequency of follow-up evaluations of the AE is left to the discretion of the investigator.

Lack of drug effect is not an AE in clinical studies, because the purpose of the clinical study is to establish treatment effect.

After the informed consent form (ICF) is signed, study site personnel will record via eCRF the occurrence and nature of each patient's preexisting conditions, including clinically significant signs and symptoms of the disease under treatment in the study. In addition, site personnel will record any change in the condition(s) and any new conditions as AEs. Investigators should record their assessment of the potential relatedness of each AE to protocol procedure investigational product, via eCRF.

The investigator will interpret and document whether or not an AE has a reasonable possibility of being related to study treatment, study device, or a study procedure, taking into account the disease, concomitant treatment or pathologies.

A "reasonable possibility" means that there is a cause and effect relationship between the investigational product, study device and/or study procedure and the AE.

The investigator answers yes/no when making this assessment.

Planned surgeries and nonsurgical interventions should not be reported as AEs unless the underlying medical condition has worsened during the course of the study.

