6.3. Handling of Dropouts or Missing Data

Intercurrent events [ICH E9(R1)] are events which occur after the treatment initiation and preclude observation of a variable or affect how it should be interpreted. Examples of such events include treatment discontinuation due to death or adverse events (AEs), rescue treatment, and loss to follow-up. This section describes missing data imputation methods handling intercurrent events, commonly used in the long-term extension studies (Ratitch 2018), which will be implemented in this study.

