6.3.2. Multiple Imputation

The multiple imputation (MI) can be used to implement the hypothetical strategy [ICH E9(R1)] for handling intercurrent events. This strategy is used to assess the effect of study treatment in a hypothetical trial where all patients have complete data and continue to take study treatment as directed without dropping out of the study or receiving rescue therapy. The MI method will be used to impute missing data with values mimicking what observations would have been had the patient not discontinued, but instead continued receiving their assigned treatment. The method assumes the data are missing at random, meaning missingness can be accounted for by collected variables. Missing outcomes for a discontinued patient are assumed to resemble those of a patient who remained in the trial and had similar baseline scores and outcomes during visits prior to the patient's discontinuation. The MI method will be the primary analysis method for longitudinal continuous outcomes and the secondary analysis for binary outcomes.

Non-monotone (that is, intermittent missingness) and monotone (that is, missingness due to treatment discontinuation) missing data will be imputed separately within each cohort under ITT population. Non-monotone missing data will be imputed using a Markov chain Monte Carlo method based on multivariate normal distribution for all outcomes. Monotone missing data will be imputed using a sequential predictive mean matching (PMM) method. The PMM method chooses a value randomly from a set of plausible observed values (e.g., in the case of sPGA, these are integers 0,1,2,3,4,5). The set consists of measured patient outcomes whose predicted values are close to the predicted value for the missing value from the simulated regression model (Heitjan and Little 1991; Schenker and Taylor 1996).

The steps of the MI method are as follows:

1. The intermittent/non-monotone missing data will be imputed with Markov chain Monte Carlo method with the imputation model based on multivariate normal distribution for the baseline and post-baseline scores. Values will be imputed until the dataset has a monotone missing pattern. Imputation will occur by calling SAS® PROC MI.

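### Modified non-responder imputation turns on the recorded discontinuation reason, so a patient who leaves because another psoriasis drug is needed may be imputed instead of counted as a non-response

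*SAP*

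**What the plan says.** SAP 6.3.4 starts from a principle: outcomes after a treatment-related exit are failures, while "Discontinuation for reasons that are considered unrelated to study treatment will not be considered a contraindication", and the outcomes after those exits are filled in by multiple imputation (MI). The working rule is then written in terms of the recorded reason. Non-response is assigned for "missing clinical response data due to discontinuation from study treatment with a reason of adverse event (AE) including death, or lack of efficacy". For everything else, "For patients discontinuing treatment with any other reason, the MI method (Section 6.3.2) will be used".

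SAP 6.3.2 describes MI as targeting a hypothetical trial in which patients "continue to take study treatment as directed without dropping out of the study or receiving rescue therapy". SAP 6.3 lists intercurrent events: "Examples of such events include treatment discontinuation due to death or adverse events (AEs), rescue treatment, and loss to follow-up".

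Protocol 8.2 contains this ground for leaving, placed with investigator decision: "If the patient, for any reason, requires treatment with another therapeutic agent that has been demonstrated to be effective for treatment of the study indication". The patient is withdrawn before the new agent starts. Section 8.2 has no entry called lack of efficacy.

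On the choice of method, Protocol 10.3.1.1 makes non-responder imputation (NRI) primary for binary endpoints and the mixed model for repeated measures (MMRM) primary for longitudinal continuous ones. SAP 6.1.3, 6.3.2 and 6.3.4 make modified NRI (mNRI) and MI primary and keep NRI as a secondary analysis.

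**The concern.** The principle in SAP 6.3.4 is about cause: was the exit related to treatment? The rule is about the label recorded. The two agree only if every exit caused by uncontrolled psoriasis is labelled lack of efficacy or adverse event. Protocol 8.2 offers a ground that describes such an exit without using either label, and the SAP does not say which category it belongs to.

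An exit of this kind recorded as investigator or patient decision goes to MI, which asks what the patient would have scored on mirikizumab without rescue. A patient withdrawn because the drug was not controlling the disease could then be imputed as a responder. Both primary endpoints, maintained sPGA (0,1) and maintained PASI 90, would be overstated to that extent.

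**Working it through.** **Figures in the plan.** There is none for this exit. The only planning figure is enrolment: (205 + 1440 + 500 + 300) = 2445; 2445 × 0.8 × 0.8 = 1565 and 2445 × 0.9 × 0.9 = 1980, which agrees with the stated 1600 to 2000. It says nothing about why patients leave, so what follows rests on assumptions.

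**Step 1: route by recorded reason.** For a patient who leaves because another agent is required for psoriasis:

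| Reason recorded | Handling under SAP 6.3.4 | In line with its principle? |
|---|---|---|
| Lack of efficacy | Non-response | Yes |
| Adverse event | Non-response | Yes |
| Investigator decision | MI | No |
| Patient decision | MI | No |

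The documents do not show which row sites would use.

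**Step 2: size.** Compared with counting these patients as non-responders, the proportion rises by s × q. Here s is the share of entry responders who left this way without lack of efficacy recorded, and q is the fraction of them that MI imputes as responders. The assumed range for s is 0.03 to 0.08.

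The values of q come from simulating the SAP's sequential predictive mean matching: 5 donors (from the SAP), 21 visits (from the protocol), regression on all earlier visits with drawn coefficients, 700 patients, 75% responders at entry, 8 replicates per scenario. Everything except the donor number and visit count is an assumption. In all scenarios the between-patient variance share was 0.3, 0.5 or 0.7 and the AR(1) correlation 0.5 or 0.8.

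- Set A, stationary disease, 24 scenarios: patients leave only when 0.5 or 1.0 SD past the response cut, with probability 0.05 or 0.15 per visit.
- Set B, permanent loss of response, 48 scenarios: worsening of 1.5 or 2.5 SD arises at 0.005 or 0.01 per visit; patients then leave with probability 0.15 or 0.5 per visit while past the cut.

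| | q, set A | q, set B | Shift over both sets |
|---|---|---|---|
| First missed visit | 0.00–0.41 | 0.04–0.40 | 0.03 × 0.00 = 0 to 0.08 × 0.411 = 3.3 points |
| Average over missed visits | 0.08–0.60 | 0.18–0.62 | 0.03 × 0.078 = 0.2 to 0.08 × 0.620 = 5.0 points |
| Last visit | 0.15–0.63 | 0.28–0.70 | 0.03 × 0.146 = 0.4 to 0.08 × 0.701 = 5.6 points |

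In set B, MI imputed 28–70% of leavers as responders at the last visit, while 2–23% would have been responders had they stayed. Two separately coded runs of set B gave imputed fractions of 21–72% and 23–65%.

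**Step 3: how demanding is the upper end?** In one of those runs, about 5–17% of entry responders left in total for loss of response. A share of 8% not coded lack of efficacy then means that about half (8/17) to all of such leavers were coded otherwise.

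**Step 4: scale.** The 95% half-width is 1.96 × √(p(1 − p)/n). With an assumed n = 1000 and p = 0.9 it is 1.9 points; with n = 300 and p = 0.8 it is 4.5 points.

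**The case against.** The strongest reply is that the rule already covers these patients. Leaving because psoriasis is uncontrolled is lack of efficacy in ordinary language. SAP 6.3.4 uses that reason although Protocol 8.2 has no such entry, so the 8.2 list cannot be the full list of recorded reasons. This stands. A reader might infer that the exit goes to MI by default, or that the rule as written contradicts its principle. The documents do not support either inference, because the conflict appears only if a site picks another category.

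Three related inferences also fail.

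- A reader might take "Lack of drug effect is not an AE in clinical studies" (Protocol 9.2) as closing a route to non-response. It closes little, because lack of efficacy is a separate route.
- A reader might say that rescue treatment has no rule. Other systemic and biologic psoriasis therapies are prohibited during treatment, and Protocol 8.2 withdraws the patient before the new agent starts. Rescue with these agents is therefore a discontinuation, which 6.3.4 handles by reason.
- A reader might infer from "No other dose adjustments are permitted in Study AMAH" (Protocol 7.4) that the 250 mg cohorts are most exposed, since only 125 mg patients may increase. That option opens only after unblinding, and the 125 mg cohort might lose response more often. No ranking of cohorts is supported.

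It is also true that NRI is scheduled for both primary endpoints (Table AMAH.6.4), that discontinuation reasons are summarised by cohort (SAP 6.5), that no hypothesis is tested (SAP 6.4), and that SAP Version 2 was approved before the study team was unblinded. These limit the harm. They do not settle the classification, because mNRI is the primary result, and NRI, which also fails every unrelated dropout, cannot isolate this group.

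On the change of primary method, a reader might infer a breach. There is none. The SAP names its primary methods openly, and Protocol 10.3.1 and SAP 6.1 place the description and justification of such changes in the study report.

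**Conclusion.** The point holds as an unresolved classification. The primary rule depends on a recorded reason, one foreseeable exit related to loss of efficacy is not assigned to a reason, and the coding is not shown. If sites record lack of efficacy, nothing is wrong. If they record investigator or patient decision, both primary maintenance proportions are biased upward relative to the SAP's own definition of failure.

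The size is unknown. Under the assumed 3 to 8% share it runs from near 0 to about 5 points at the last visit (upper values 5.0 in the stationary scenarios and 5.6 with permanent loss), with smaller values at the first missed visit. The share is an assumption with no support in the documents. With the reporting already planned, this is a cheap improvement to the primary rule and does not threaten the study's conclusions. The difference between protocol and SAP primary methods is a minor disclosure matter.

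**What to change.** In SAP 6.3.4, state that a discontinuation made because another therapy is required for psoriasis counts as non-response in mNRI, whatever disposition category is recorded. Identify it from the recorded reason or comment. Do not infer it from therapy started in follow-up alone, since Protocol 5.1.3 allows that for every patient. Exclude agents needed for another condition, which the wording of Protocol 8.2 would otherwise bring in.

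If nothing finer than the category is collected, report how many exits in each category were sent to MI, and show NRI beside mNRI for both primary endpoints.

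For disclosure, say in the study report, and preferably in the SAP, that mNRI and MI replace the protocol's NRI and MMRM as primary methods, and why.

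The cost is one classification sentence, one disclosure sentence and a short review of recorded reasons. No protocol amendment is needed. The headline proportion may be slightly lower.

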6.4. Multiple Comparisons/Multiplicity

The analysis will be focused on point estimates and confidence intervals. Thus, no hypothesis testing will be performed, and adjustments due to multiple testing is not to be accounted for.

6.5. Patient Disposition

A detailed description of patient disposition from the study will be listed by timing and summarized with reasons for discontinuation by cohort for the ITT population. Frequency counts and percentages of patients discontinuing the treatment and study will be presented.

6.6. Patient Characteristics

Patient demographic variables, baseline characteristics and baseline clinical measures will be summarized for the baseline of the originating study and, for measurements that are expected to change over time, Visit 1 of Study AMAH by the cohorts described in Section 6.1.1.

Table AMAH.6.2 describes the specific variables and how they will be summarized. The summary of additional patient characteristics and subgroup analysis will not require an amendment to the SAP.

Table AMAH.6.2. Patient Characteristics

Variable	Quantitative Summary	Categorical Summary	Baseline Summary	
			Originating Studies	Study AMAH
Demographic Characteristics				
Age ^a	Yes	<65 years, ≥65 years	X	X
		<40 years, ≥40 years	X	X
Sex	No	Male, Female	X	
Age within Sex	No	Male <40 years, Male ≥40 years, Female <40 years, Female ≥40 years	X	X
Ethnicity	No	Hispanic/Latino, Non-Hispanic/Non-Latino	X	
Race	No	American Indian/Alaska Native, Asian, Black/African American, Native Hawaiian or other Pacific Islander, White, or Multiple	X	
Geographic Region	No	North America (Canada, Puerto Rico, United States), Europe (Czech Republic, France, Germany, Hungary, Italy, Poland, Spain, United Kingdom), Other (Argentina, Australia, Israel, Japan, Korea, Mexico, Russia, Taiwan)	X	X
	No	By Country	X	X
	No	Asia (Israel, Japan, Korea, Taiwan), North America (Canada, Puerto Rico, United States), Australia, Central America/South America (Argentina, Mexico), Europe (Czech Republic, France, Germany, Hungary, Italy, Poland, Russia, Spain, United Kingdom)	X	X
Height (cm)	Yes	None	X	

Variable	Quantitative Summary	Categorical Summary	Baseline Summary	
			Originating Studies	Study AMAH
Weight (kg)	Yes	<80 kg, ≥80 kg	X	X
		<100 kg, ≥100 kg	X	X
BMI ^b	Yes	Underweight (<18.5 kg/m ²), Normal (≥18.5 and <25 kg/m ²), Overweight (≥25 and <30 kg/m ²), Obese (≥30 and <40 kg/m ²), Extreme obese (≥40 kg/m ²)	X	X
Alcohol use	No	Never, Current, Former	X	X
Caffeine use	No	Never, Current, Former	X	X
Tobacco use	No	Never, Current, Former	X	X
Prior Psoriasis Therapy				
Prior systemic therapy ^d	No	Never used, Ever used	X	
Prior biologic therapy ^e	No	Never used, Ever used	X	
Number prior biologics	No	0, 1, 2, >2	X	
Prior non-biologic systemic therapy ^d	No	Never used, Ever used	X	
Number of non-biologic systemic therapies ^d	No	0, 1, 2, >2	X	
Psoriasis Duration and Age at Onset				
Duration of psoriasis (years) ^e	Yes	<15, ≥15	X	X
Duration of diagnosis (years) ^f	Yes	None	X	X
Age at onset (years) ^g	Yes	<25, ≥25	X	
Area of Involvement				
Facial involvement	No	Yes, No	X	
Nail involvement	No	Yes, No	X	
Scalp involvement	No	Yes, No	X	
Palmoplantar involvement	No	Palm involvement only, Sole Involvement only, Both, either	X	
		Yes, No	X	
Baseline Psoriatic Arthritis	No	Yes, No	X	

Variable	Quantitative Summary	Categorical Summary	Baseline Summary	
			Originating Studies	Study AMAH
Baseline Disease Severity				
Baseline PASI score	Yes	<20, ≥20	X	
		<15, ≥15	X	
Baseline sPGA score	No	Clear (0), Minimal (1), Mild (2), Moderate (3), Severe (4), or Very severe (5)	X	
Baseline BSA (%)	Yes	<20%, ≥20%	X	
Baseline PSSI	Yes	None	X	
Baseline NAPSI	Yes	None	X	
Baseline PPASI	Yes	None	X	
Baseline PSS sign scores	Yes	0, 0 to 1, ≥1	X	
Baseline PSS symptom score	Yes	0, 0 to 1, ≥1	X	
Baseline DLQI total score	Yes	0 or 1, >1	X	
		≤10, >10	X	
		<5, ≥5	X	

Abbreviations: BMI = body mass index; BSA = body surface area; eCRF = electronic case report form; IL-17 = interleukin 17; MCS = mental component score; NAPSI = Nail Psoriasis Severity Index; PASI = Psoriasis Area and Severity Index; PCS = physical component score; PPASI = Palmoplantar Psoriasis Severity Index; PSS = Psoriasis Symptoms Scale; PSSI = Psoriasis Scalp Severity Index; PUVA = psoralen and ultraviolet A; sPGA = Static Physician Global Assessment; TNF = tumor necrosis factor; UVB = ultraviolet B.

- ^a Age in years will be calculated as length of the time interval from the imputed date of birth (July 1st in the year of birth collected in the eCRF) to the informed consent date.
- ^b Body Mass Index (BMI) will be calculated as: $BMI (kg / m^2) = Weight (kg) / (Height (m))^2$.
- ^c Biologic systemic therapies include: Efalizumab, Ustekinumab, Infliximab, Etanercept, Alefacept, Adalimumab, Golumumab, Certolizumab pegol, Secukinumab, Ixekizumab, Brodalumab, and other biologic agents.
- ^d Non-biologics systemic therapies include: Cyclosporine, Methotrexate, Corticosteroids, Acitretin, Fumaric acid derivatives, Apremilast, other systemic agents, and psoralen and ultraviolet A (PUVA).
- ^e Duration of psoriasis is calculated as: (date of informed consent – date of psoriasis onset)/365.25.
- ^f Duration of psoriasis diagnosis is calculated as: (date of informed consent – date of psoriasis diagnosis)/365.25.
- ^g Age at diagnosis in years will be calculated as the time interval from the imputed date of birth (July 1st in the year of birth collected in the eCRF) to the date of psoriasis diagnosis.

